7.3	ENDOSCOPIC ASSESSMENT	15
7.4	HISTOLOGICAL ASSESSMENT	16
7.4.1	SAMPLING AND SHIPMENT PROCEDURES	16
7.4.2	HISTOLOGICAL CRITERIA FOR DIAGNOSIS OF MC AND SUBTYPES	16
7.5	ASSESSMENT OF BIOLOGICAL MARKER	18
7.5.1	ASSESSMENT OF FECAL CALPROTECTIN LEVELS	18
7.5.2	ASSESSMENT OF FECAL EPC AND EPX LEVELS	18
8	ENDPOINTS	19
8.1	PRIMARY ENDPOINT	19
8.2	SECONDARY ENDPOINTS	19
8.3	DEFINITIONS OF INTEREST	19
8.3.1	CLINICAL OUTCOMES (APPLICABLE TO ALL MC SUBTYPES – CC, LC AND IC)	19
8.3.2	HISTOLOGICAL OUTCOMES	20
9	STATISTICAL ANALYSIS	20
9.1	GENERAL CONSIDERATIONS	20
9.2	SAMPLE SIZE	22
10	ETHICAL AND LEGAL ASPECTS	22
10.1	ETHICS	22
10.2	INFORMED CONSENT	22
10.3	STUDY DISCONTINUATION CRITERIA	22
11	QUALITY CONTROL	23
12	DATA HANDLING	23
12.1	CONFIDENTIALITY	23
12.2	DATA COLLECTION	23
12.3	STUDY ARCHIVE	24
12.4	PUBLICATION POLICY	24
13	REFERENCES	25
14	APPENDIX – CRONOGRAM	27

1. Sinopse

Title:	An epidemiological study to determine the prevalence of Microscopic Colitis and describe its clinical and histological features among patients with symptoms of chronic watery diarrhea submitted to colonoscopy attending to the Portuguese gastroenterology setting
Study Code:	MICRA
Scientific Coordinator:	[name]
Disease/Condition:	Microscopic Colitis
Rational:	
There's a lack of epidemiological data regarding Microscopic Colitis (MC) in Portugal, including prognosis factors and therapies used to treat this condition. Therefore, it becomes pertinent to characterize this population and, simultaneously, to evaluate the key characteristics that distinguish this clinical entity from other conditions among a population who attends a gastroenterology setting with symptoms of chronic watery diarrhea.
 
This study aims to estimate the prevalence of MC and its subtypes among patients who attend a gastroenterologist appointment due to chronic, watery diarrhea of unknown etiology and who are eligible to colonoscopy. In addition, socio-demographic, clinical characteristics and treatment patterns will be described for patients with confirmed diagnosis of MC and these features will be compared with non-MC cases. Furthermore, this study will prospectively assess the clinical and histological progression of MC patients during a follow up period of 2 years. Potential biomarkers for this condition will also be explored.

Research hypothesis:	No research hypothesis was defined
Primary Objectives:	To determine the prevalence of MC among patients who attend a specialist appointment with symptoms of chronic, watery diarrhea of unknown etiology for more than 4 week and undergo colonoscopy.
Secondary Objective(s):	
 • To determine the prevalence of MC subtypes (collagenous colitis, lymphocytic colitis and incomplete colitis) • To compare the socio-demographic, clinical and histological characteristics and previous therapies of patients with confirmed diagnosis of MC (MC patients) versus patients without diagnosis of MC (non-MC patients) • To describe the therapeutic attitude regarding MC patients over a period of 24 months • To describe the clinical activity of MC patients over a period of 24 months. • To describe the histological features of MC patients 24 months after diagnosis. • To explore the association of socio-demographic, clinical and histological characteristics with clinical activity among MC patients followed for 24 months. • To explore the association of socio-demographic, clinical characteristics with histological activity among MC patients followed for 24 months. • To explore the correlation of treatments used by MC patients with clinical activity. • To explore the correlation of treatments used by MC patients with histological activity. • To explore the correlation between fecal calprotectin, EPC and EPX levels with clinical activity among MC patients
Study Design:	This is a multicenter, cross-sectional, observational study aiming to determine the prevalence of MC among a consecutive sample of subjects who attend a specialist consultation with symptoms of chronic watery diarrhea and who are eligible to colonoscopy. In addition, the study design contemplates a 24-month prospective

	
component with repeated measures for all MC patients with confirmed diagnosis of MC in order to investigate the clinical and histological progression.
 
There is no imposed experimental intervention or treatment in this study. All therapeutic decisions and management of subjects will be done according to routine clinical practice.

Inclusion Criteria:	
 1. Patients who signed the informed consent; 2. Male or female patients, 18 years or older; 3. Patients with chronic or intermittent, watery diarrhea of unknown etiology for more than 4 weeks; 4. Patients who are eligible for complete colonoscopy according to physician's clinical criteria.
Exclusion Criteria:	
 1. Patients with history of IBDs or any other known intestinal disease. 2. Any condition that precludes the patient to undergo complete colonoscopy. 3. Patients who are being treated with any investigational agent; 4. Pregnancy 5. Patients who are not willing to comply with routine clinical appointments or procedures
Expected number of subjects:	300
Expected number of sites:	Approximately 10 centers are expected to participate.
Subject selection:	All subjects who meet eligibility criteria and give their written informed consent to participate will be consecutively enrolled and characterized regarding several socio-demographic and clinical characteristics of interest. All eligible subjects will undergo a colonoscopy according to the routine practice for this type of population.
Exposure of interest:	Not applicable
Main data collected:	At first appointment socio-demographic, clinical, endoscopic, histologic data will be collected for all eligible patients. Patients with confirmed diagnosis of MC will be followed during 24 months. During this period, clinical and histological data will be collected.
Endpoints	
Primary endpoint: Number of patients with confirmed diagnosis of MC (any subtype) over the total number of colonoscopies performed in all patients included in the study.
 
Secondary endpoints:
 
 •Proportion of patients with confirmed diagnosis of each subtype of MC (CC, LC and IC) •Age, gender, BMI, smoking status, duration of symptoms, stool frequency and consistency (type), familial history of IBDs, comorbidities, previous pharmacological/ non-pharmacological therapies and laboratory parameters will to be compared between MC patients and non-MC patients. •Treatments (pharmacological/non-pharmacological) prescribed by specialist for patients with MC diagnosis •Number of stools and type (Bristol stool form scale), urgency and abdominal pain over the last 7 days before each time point of assessment for patients with MC diagnosis. •Proportion of MC patients with clinical remission at each data collection time point (month 3, 6, 9, 12, 15, 18, 21 and 24) Clinical remission: mean of < 3 stools per day and mean of < 1 watery stool per day •Proportion of MC patients with histological remission at month 24. See section 8.3.2 for definition of histological remission •Age, gender, BMI, smoking status, duration of symptoms, stool frequency and consistency, familial history of IBDs, age at diagnosis of MC, time to diagnosis of MC, comorbidities, pharmacological/non-pharmacological therapies, laboratory parameters and histological features, compared with clinical activity status (active/non active) described for patients with MC diagnosis. •Age, gender, BMI, smoking status, duration of symptoms, stool frequency and

	
consistency, familial history of IBDs, age at diagnosis of MC, time to diagnosis of MC, comorbidities, pharmacological/non-pharmacological therapies, laboratory parameters, compared with histological features, described for patients with MC diagnosis.
 
 •Area under the ROC curve of fecal calprotectin, ECP and EPX levels with clinical activity at each data collection time points among MC patients. •Area under the ROC curve of fecal calprotectin ECP and EPX levels with histological activity at each data collection time points among MC patients.
Statistical methods	
The association between two quantitative variables will be performed through Pearson correlation coefficient or Spearman correlation coefficient, in case the normality assumption is not verified.
 
The association of two categorical variables will be tested through the Chi-Square test or Fisher Exact test (if applicable).
 
The comparison of two independent samples in respect to quantitative variables will be performed through t-test for independent samples or the Mann-Whitney non-parametric test, according to the assumption validations of the statistical test (if applicable).
 
The proportion of patients with clinical remission and histological remission (overall, by MC subtype and colonic segment) at each data collection time points will be summarized using 95% confidence intervals.
 
Area under the ROC curve will be used to correlate numerical variables with binary categorical variables. A high discriminatory ability will be considered for values > 0.75.
 
Repeated Measures Analysis or Generalized Estimated Equations will be used to investigate the evolution profile of clinical and histological characteristics throughout the data collection time points (time-effect).
 
Generalized Estimated Equations will be used to explore the association between clinical (as independent variable) and histologic features (as dependent variable) observed within-patients.

Overall Study Duration:	
The overall duration of the study is three years (1 year of recruitment + 2-year observation period).

Study timelines:	
The study is expected to start during the 1th Quarter of 2015. Study closure is expected to occur in the 2st Quarter of 2018.

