2.2 BIOMARKERS IN MICROSCOPIC COLITIS

Given the invasive nature of endoscopy, the implementation of an easy, non-invasive method to support the pre-diagnostic screening and monitoring of disease activity is essential.

An increased prevalence of autoimmune serological tests has been found in MC patients but no clinically useful marker for the disease has yet been identified.³

The faecal markers evaluated so far in MC include a variety of substances/proteins that either leak from or are generated by the inflamed mucosa in the gut. Proteins studied include lactoferrin, myeloperoxidase (MPO), calprotectin, eosinophil cationic protein (ECP) and eosinophil protein X (EPX), as indicators of neutrophilic, macrophage and eosinophil activation. Likewise, studies of tryptase, occult blood and cytokines have been performed.²⁵ Faecal calprotectin has been shown to be useful in the diagnosis of IBD, correlates with mucosal disease activity and can help to predict response to treatment or relapse. In IBD, the presence of active gut inflammation is associated with migration of leucocytes, including neutrophils, to the gut mucosa.²⁶ As a result the faecal stream contains increased levels of these inflammatory proteins including calprotectin. Faecal calprotectin has been shown to differentiate quiescent from active disease in both patients with CD and UC.^{27,28}

Overall, 52 patients with MC have been investigated for faecal calprotectin in five different studies, of whom 71% (n=37) had positive samples.²⁹⁻³³ In two cohorts calprotectin was significantly increased compared to healthy controls and decreased significantly when remission was induced. On the other hand, in the two studies no correlation was found between calprotectin levels and disease activity (measured by bowel frequency), stool consistency and histological grade of inflammation in mucosal biopsies.^{32,33}

Overall ECP and EPX have been examined in 15 and 33 patients with active CC, respectively.^{32,34,35} In the study of Lestejo et al., 2006, 18 patients with CC were compared with patients with IBDs and healthy controls in order to elucidate whether EPX in combination with other faecal markers could be used to distinguish between these disorders. Eleven patients (61%) had EPX values above the upper limit of normal, and values were significantly higher than in IBDs and healthy controls.³⁴

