In the study of Wagner et al., 2011, ECP and EXP were positive in 11 and 8 out of 12 patients with active CC disease, respectively, and became normal in all patients when remission was induced with budesonide.³²

In spite of the small samples analyzed, ECP and EXP may be promising faecal markers.³⁶

The association of faecal calprotectin, ECP and EXP with clinical and histological features in MC patients will be explored in this study.

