3.2 SECONDARY OBJECTIVES

- To determine the prevalence of MC subtypes (CC, LC and IC)
- To compare the socio-demographic, clinical and histological characteristics and previous therapies of patients with confirmed diagnosis of MC (MC patients) versus patients without diagnosis of MC (non-MC patients)
- To describe the therapeutic attitude regarding MC patients over a period of 24 months
- To describe the clinical activity of MC patients over a period of 24 months.
- To describe the histological features of MC patients 24 months after diagnosis.
- To explore the association of socio-demographic, clinical and histological characteristics with clinical activity among MC patients followed for 24 months.
- To explore the association of socio-demographic, clinical characteristics with histological activity among MC patients followed for 24 months.
- To explore the correlation between the treatments used by MC patients and clinical activity.
- To explore the correlation between the treatments used by MC patients and histological activity.

- To explore the correlation between fecal calprotectin, EPC and EPX levels and clinical activity among MC patients.
- To explore the correlation between fecal calprotectin, EPC and EPX levels and histological activity among MC patients.

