9 STATISTICAL ANALYSIS

9.1 GENERAL CONSIDERATIONS

All quantitative variables will be summarized through descriptive statistics namely mean, median, standard deviation and range (minimum and maximum) and qualitative variables through absolute (n)

and relative frequencies (%) and 95% confidence intervals (if applicable). The statistical analysis will be performed through frequency tables for qualitative variables and tables with descriptive statistics for quantitative variables.

The association between two quantitative variables will be performed through Pearson correlation coefficient or Spearman correlation coefficient, in case the normality assumption is not verified.

The association of two categorical variables will be tested through the Chi-Square test or Fisher Exact test (if applicable).

The comparison of two independent samples in respect to quantitative variables will be performed through t-test for independent samples or the Mann-Whitney non-parametric test, according to the assumption validations of the statistical test (if applicable).

The proportion of patients with clinical remission and histological remission (overall, by MC subtype and colonic segment) at each data collection time points will be summarized using 95% confidence intervals.

Area under the ROC curve will be used to correlate numerical variables with binary categorical variables. A high discriminatory ability will be considered for values > 0.75 .

Repeated Measures Analysis or Generalized Estimated Equations will be used to investigate the evolution profile of clinical and histological characteristics throughout the data collection time points (time-effect).

Generalized Estimated Equations will be used to explore the association between clinical (as independent variable) and histologic features (as dependent variable) observed within-patients.

The association analysis of fecal calprotectin, EPC and EPX with clinical activity

- The association between fecal calprotectin levels EPC and EPX with clinical activity (remission/active disease) will be analyzed through Area Under the ROC Curve at each data collection time point (diagnosis and every 3 months up to month 24).

The association analysis of fecal calprotectin EPC and EPX with histological features

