- The association between fecal calprotectin, EPC and EPX levels with histological features (collagen thickness [$\leq 5 \mu\text{m}$; $> 5 \mu\text{m}$], inflammation [Geboes grade < 3.1 ; grade ≥ 3.1] and IEL count [$\leq 5 \text{ IEL}/100$; $> 5 \text{ IEL}/100$ surface epithelial cells) will be analyzed through Area Under the ROC Curve at each data collection time point (diagnosis and month 24).

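### The serial fecal marker data are analysed against clinical activity one visit at a time, so how well a marker follows a patient's own activity is never estimated

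*Protocol*

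**What the plan says.** **Rationale.** Section 2.2 states that "the implementation of an easy, non-invasive method to support the pre-diagnostic screening and monitoring of disease activity is essential". Among its evidence for eosinophil cationic protein (ECP) and eosinophil protein X (EPX) is a small study in collagenous colitis, in which the markers "became normal in all patients when remission was induced with budesonide".

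**Objective.** Section 3.2 is more modest: "To explore the correlation between fecal calprotectin, EPC and EPX levels and clinical activity among MC patients". It does not say whether the association is within or between patients.

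**Data.** Section 7.5 and the Appendix schedule calprotectin, ECP and EPX at diagnosis and at months 3, 6, 9, 12, 15, 18, 21 and 24. That is up to nine values per MC patient. Stool data, which define activity in section 8.3.1, are collected on the same schedule.

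**Analysis.** The endpoint in the Synopsis and section 8.2 is "Area under the ROC curve of fecal calprotectin, ECP and EPX levels with clinical activity at each data collection time points among MC patients". Section 9.1 repeats that the association with clinical activity "will be analyzed through Area Under the ROC Curve at each data collection time point (diagnosis and every 3 months up to month 24". For histological features the same method is used at two time points: "will be analyzed through Area Under the ROC Curve at each data collection time point (diagnosis and month 24". The yardstick is "A high discriminatory ability will be considered for values > 0.75".

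**Repeated-measures methods.** Section 9.1 has two such lines. One models the course over time of clinical and histological characteristics. The other uses GEE to relate clinical to histologic features within patients. Neither names the markers.

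**The concern.** A per-visit AUC asks whether, on one day, an active patient tends to have a higher marker value than a different patient in remission. Monitoring asks whether a patient's marker is higher when that same patient is active. The two answers coincide only when patients share much the same usual level. Otherwise stable differences between patients blur the per-visit comparison and leave the within-patient one untouched.

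Section 2.2 itself reports that calprotectin fell when remission was induced, and that in two studies it did not correlate with activity. That pattern is compatible with a marker that follows change within patients better than it separates patients. The planned analysis cannot tell these apart.

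Two things are at stake. Serial samples are used as nine unconnected cross-sections of about 30 patients each. And a marker that tracks activity within patients could miss the 0.75 label and be set aside for monitoring on the wrong evidence.

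**Working it through.** **1. Number of patients.** Section 9.2 gives 300 subjects and a lowest prevalence of 10%: 300 × 0.10 = 30 MC patients, as stated. Its precision also reproduces: 1.96 × √(0.10 × 0.90 / 300) = 3.4% and 1.96 × √(0.15 × 0.85 / 300) = 4.0%, both under 4.5%. It gives no figure for the marker AUCs.

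**2. Precision of one visit.** With 30 patients and a true AUC of 0.75, the Hanley-McNeil 95% half-width is about 0.18 (15 active, 15 in remission), 0.20 (10 and 20) or 0.24 (6 and 24). The splits are assumptions.

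**3. Link between the two AUCs.** Assume log marker = patient level + shift when active + visit noise, all normal. ICC is the share of variance, at a given activity state, that lies between patients.

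- Within-patient AUC = Φ(shift / (√2 × within-patient SD))
- Per-visit AUC = Φ(z × √(1 − ICC)), where z is the normal quantile of the within-patient AUC

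For a within-patient AUC of 0.90, z = 1.2816:

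| ICC | z × √(1 − ICC) | Per-visit AUC |
|---|---|---|
| 0 | 1.282 | 0.90 |
| 0.5 | 0.906 | 0.82 |
| 0.7 | 0.702 | 0.76 |
| 0.8 | 0.573 | 0.72 |
| 0.9 | 0.405 | 0.66 |

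The expected per-visit AUC reaches 0.75 at ICC = 1 − (0.6745 / 1.2816)² = 0.72. For within-patient AUCs of 0.80, 0.85 and 0.95 the crossing is at 0.36, 0.58 and 0.83.

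**4. Simulation of the label.** With 30 patients, 8 visits, 50% active (independent between visits), within-patient AUC 0.90 and 1,500 runs, a single visit's AUC was 0.75 or less in 1%, 19%, 44% and 64% of cases at ICC 0, 0.5, 0.7 and 0.8. The within-patient AUC pooled over visits averaged 0.90 and was never 0.75 or less.

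**5. Power, and where the gain comes from.** A second set of assumptions fixes total variance at 1.25 and the shift at 0.8. The per-visit AUC is then Φ(0.8 / √2.5) = 0.69 at every ICC, and within-patient concordance is 0.69, 0.76 and 0.87 at ICC 0, 0.5 and 0.8. With 30 patients, 8 visits, 40% active and a latent correlation of activity of 0.4, a Mann-Whitney test at one visit had 41–43% power. The within-patient comparison over all visits had 98–100%, using about 25 of the 30 patients. At ICC 0, with no spread between patients to remove, the figures were already 43% and 98%. So 98 − 43 = 55 points of a gain of at most 100 − 41 = 59 come from using all visits.

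**6. Other planned analyses.** Section 7.1 lists the fecal sample among baseline characteristics introduced as socio-demographic and clinical, so markers could be read into the repeated-measures lines of section 9.1. On that reading the protocol would give a marker's time course, or its relation to histology, but still no model of marker against clinical activity. The Pearson/Spearman line concerns two quantitative variables and does not address repeated measures; activity is binary.

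**The case against.** The strongest reply is that the planned AUC answers the objective as written. Section 3.2 asks only to explore a correlation, no hypothesis is defined, and monitoring appears in one background sentence beside pre-diagnostic screening. This stands: the mismatch is with the rationale and the serial sampling, not with the wording of the objective.

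A second reply is that a clinic using one cut-off for everyone needs the between-patient AUC. Section 2.2 partly cites markers as positive or above a normal limit, which is a comparison with a common limit. Stable differences between patients are then real misclassification. This also stands, and it is why the per-visit AUCs should stay.

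A third reply is that extra models belong in the SAP. That carries less weight, because section 9.1 already fixes the method for this endpoint and what it fixes leaves the repeated measures unused.

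Some stronger readings are tempting but not supported:

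- **A good tracking marker will be reported as poor.** The protocol defines only a high label and attaches no consequence to missing it. At ICC 0 there is no loss, and at ICC 0.5 a within-patient AUC of 0.90 still gives an expected 0.82.
- **The power gap measures the harm from between-patient spread.** Step 5 shows that most of it does not.
- **Activity based on reported stool counts invalidates the AUC for monitoring.** The same status would enter the added model, so the argument does not favour one over the other, and AUCs against histology are also planned.
- **A lagged analysis predicting the next visit is required.** The protocol mentions predicting relapse only for inflammatory bowel disease, and with about 30 patients nothing shows that such an analysis would be informative.

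**Conclusion.** The concern holds in a limited form. The only analysis fixed for marker against clinical activity is a separate between-patient AUC at each visit. It uses about 30 patients at a time, with a half-width near 0.2, and leaves within-patient tracking unestimated although the data for it are collected.

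The understatement is conditional. For an assumed within-patient AUC of 0.90 it runs from none at ICC 0 to an expected 0.72 at ICC 0.8, and the 0.75 mark is crossed at an ICC of about 0.72. More patients would narrow the interval but not remove this difference. The ICC, the shift and the share of active visits are all assumptions, since the protocol gives none of them. The surer gain is that all visits are used. This affects an exploratory secondary endpoint; the prevalence estimate is not touched.

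**What to change.** Keep the per-visit AUCs as description. In sections 8.2 and 9.1 add one analysis per marker that uses all visits:

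- a linear mixed model of log marker on activity status, split into the patient's own mean over visits and the deviation from that mean, with visit as a factor and a patient random intercept;
- the within-patient concordance, which is the share of pairs of one active and one remission visit of the same patient in which the marker is higher at the active visit, with a bootstrap interval that resamples patients;
- the number of patients who contribute to it.

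State that any conclusion about monitoring rests on this within-patient estimate. A lagged analysis of marker against activity at the next visit may be listed as optional and exploratory.

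The cost is a few lines of text and a little programming, with no new data or visits. The downside is that patients who are always active or always in remission add nothing to the within-patient estimate.
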